### **Clinical Laboratory Evaluations**

Normal ranges for each study center will be tabulated. Scheduled laboratory tests will be summarized. Unscheduled follow-up tests performed for medical or safety concerns, will be listed only. Test results will be presented using shift tables, showing the change in laboratory values from baseline to each subsequent visit. Accompanying scatter plots and line plots will have a different symbol or color for each treatment arm. All summary analyses will be conducted by treatment group using the as-treated population.

Descriptive statistics will be presented by treatment group and visit week for the laboratory measurements. Continuous laboratory measures will also be compared to reference ranges to determine whether they are abnormally high, low, or normal. The incidence and percent of high, low and normal values will be listed for each of the treatment arms. For subjective (qualitative) laboratory assessments, count and percent of normal and abnormal values will be presented. For laboratory values that are entered as outside the detectable range for a laboratory, the midpoint of the undetectable range will be used for analyses and nonparametric analyses will be performed.

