- Patients with NCCN very low risk prostate cancer (· T1c and Grade Group 1 (Gleason 6) and PSA <10 ng/mL and Fewer than 3 prostate biopsy fragments/cores positive, ≤50% cancer in each fragment/coreg and · PSA density <0.15 ng/mL/g) can be monitored without intervention and enrolled in study.
- Patients with NCCN low risk prostate cancer can be monitored on a case by case basis (T1-T2a and Grade Group 1 (Gleason 6) and · PSA <10 ng/mL) and enrolled in study.
- All other patients should be excluded.

12. History of LFT abnormalities as outlined below, or imaging, laboratory or other clinical information suggesting liver dysfunction, advanced liver disease or cirrhosis. Evidence of hepatic impairment that in the opinion of the investigator could interfere with drug metabolism or increase the risk of the known hepatotoxicity of study drug.

Any of the following liver function abnormalities:

- a. Total bilirubin above the upper limit of normal (ULN), excluding patients with Gilbert's syndrome;
- b. Aspartate or alanine aminotransferase (AST/SGOT or AST/SGPT) > 3 X ULN;
- c. Alkaline phosphatase > 2.5 X ULN.

13. History of end-stage renal disease requiring dialysis

14. History of unstable or deteriorating cardiac disease, or unstable cardiac arrhythmia or arrhythmia requiring modification of drug therapy, myocardial infarction within the previous year, heart failure requiring hospitalization.

15. Any condition that, in the opinion of the investigator, might be significantly exacerbated by the known side effects associated with the administration of pirfenidone

16. History of alcohol or substance abuse in the past 2 years, at the time of Screening

17. Family or personal history of long QT syndrome

18. Any of the following test criteria above specified limits:

- a. Estimated glomerular filtration rate <30 mL/min/1.73m^2
- b. ECG with a QTc interval >500 msec at Screening

19. Prior use of pirfenidone or known hypersensitivity to any of the components of study treatment

20. Use of any of the following therapies within 28 days before Screening and during participation in the study:

- a. Investigational therapy, defined as any drug that has not been approved for marketing for any indication in the country of the participating site
- b. Potent inhibitors of CYP1A2 (e.g. fluvoxamine, enoxacin)
- c. Potent inducers of CYP1A2.
- d. Sildenafil (daily use). Note: intermittent use for erectile dysfunction is allowed

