**Table 1. Recommended Procedures for Participants with Elevated Liver Aminotransferase Test Results**

Magnitude of Elevation in ALT or AST	Recommendation

>3 to ≤5 × ULN  Not accompanied by symptoms or hyperbilirubinemia                      (Total bilirubin >2 × ULN)
	
Exclude other causes (e.g. confounding medications).
 
Monitor the patient closely, including repeat liver chemistry tests. If clinically appropriate, reduce or interrupt the dose (e.g., until liver chemistry test results are within normal limits). Once liver function tests are again within normal limits, Esbriet may be re-titrated to the recommended daily dose if tolerated.
 
Liver function tests should be repeated at 1 month intervals until < 3 x ULN

>3 to ≤5 × ULN  Accompanied by hyperbilirubinemia                      (Total bilirubin >2 × ULN) or  clinical signs or symptoms of liver injury*
 
*Refer to section 6.1.19 for clinical signs of symptoms
	
Study treatment should be permanently discontinued. Liver function tests should be monitored monthly until symptoms resolve and bilirubin < 2 x ULN

>5 × ULN
	
Study treatment should be permanently discontinued. Liver function tests should be monitored monthly until < 3 x ULN

ALT = alanine aminotransferase; AST = aspartate aminotransferase; ULN = upper limit of normal

In the event of a QTc >500 msec, refer to Section 7.1.2 for instructions.

With the exceptions noted above, study treatment may be restarted at the discretion of the investigator. For treatment interruptions of ≥28 days, a pre-restart visit is required, as outlined in Section 6.1.8, in addition to study treatment titration.

Investigators should use the flowchart in Appedix B to re-titrate subjects to full dose. However if the subject is unable to tolerate the full dose, the subject will be maintained on the highest dose tolerable for the remainder of the study. Dosing changes and interruptions will be recorded.

In participants requiring hospitalization for an acute pulmonary process of unclear etiology, the investigator should consider continuing study treatment, if appropriate. If the participant is hospitalized at an institution other than the study site, the treating physician should be encouraged

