#### **6.1.9 Precautionary Measures**

Drug-induced liver injury (DILI) has been observed with pirfenidone. In the postmarketing period, non-serious and serious cases of DILI, including severe liver injury with fatal outcome, have been reported. Patients treated with pirfenidone had a higher incidence of ALT and/or AST elevations of  $\geq 3x$  ULN (3.7%) compared with placebo patients (0.8%). Increases in ALT and AST  $\geq 3x$  ULN were reversible with dose modification or treatment discontinuation.

Measure liver function promptly in patients who report symptoms that may indicate liver injury, including fatigue, anorexia, right upper abdominal discomfort, dark urine, or jaundice. Dosage modification or interruption may be necessary for liver enzyme elevations. See Table 1.

Pirfenidone is causally associated with DILI, mainly in the form of transient liver enzyme elevations of no clinical relevance. However, clinical manifestations of DILI including cases with fatal outcome – possibly caused by idiosyncratic reactions to pirfenidone – have been reported in rare instances.

Exposure to sunlight (including sunlamps and tanning beds) should be avoided or minimized during study treatment due to the possibility of photosensitivity reactions or rash. Participants should be instructed to use sunscreens that have a sun protection factor (SPF) of 50 or higher as well as protection against ultraviolet A (UV-A) radiation, and also to wear clothing that protects against sun exposure and avoid concomitant medications known to cause photosensitivity reactions, if possible.

All doses of study treatment are to be taken with food to reduce the likelihood of gastrointestinal symptoms. The dose titration period of 21 days at the initiation of study treatment is designed to maximize tolerability.

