### **Appendix C SAFETY REPORTING DEFINITIONS AND CONTACTS**

The definitions below are based on the International Conference on Harmonization (ICH) guidelines and Food and Drug Administration (FDA) regulations. The use of italic font in this section refers to definitions taken from ICH guidelines and/or FDA regulations. Other definitions relate to company specific glossaries.

- **Adverse Drug Reaction (ADR)**

In the pre-approval clinical experience or in other clinical trial experiences:

Any noxious and unintended response to a medicinal product related to any dose will be considered an ADR.

The phrase "responses to a medicinal product" or "associated with the use of the medication," means that a causal relationship between a medicinal product and an adverse event is at least a reasonable possibility, i.e., the relationship cannot be ruled out.

- **Adverse Event (AE)**

Any untoward medical occurrence in a patient or clinical investigation subject administered a pharmaceutical product and which does not necessarily have to have a causal relationship with this treatment. An AE can therefore be any unfavorable and unintended sign (including an abnormal laboratory finding, for example), symptom, or disease temporally associated with the use of a medicinal product, whether or not considered related to the medicinal product.

- **Awareness Date**

The date any Party (including employees of affiliates or agents acting on behalf of either Party), first has knowledge of the minimum data elements as defined by ICH E2A guideline. At the very least, the following data must be provided for a case to be considered as valid:

- an identifiable reporter\*
- an identifiable patient\*\* (i.e., either CRF number, patient/subject number, initials, gender, date of birth, age or age group)
- a drug / counterfeit drug
- an adverse event (or pregnancy)

\*For AE reports from social media sources, verified contact details (e.g., email address) are considered an identifiable reporter.

\*\*For reports from healthcare professionals, "a patient" is considered an identifiable patient criterion.

The minimum data elements should be obtained initially prior to transmitting the information to the other Party. In the event that an AE/ADR or pregnancy report is lacking minimum data elements, this report should not be forwarded to the other Party until all the minimum data elements are gathered.

The originating Party will ensure prompt follow-up as necessary.

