## **Adverse Events**

An AE is any untoward medical event associated with the use of a drug in humans, whether or not it is considered related to a drug. Adverse events will be coded from the actual term described by the investigator using the Medical Dictionary for Regulatory Activities (MedDRA).

Treatment-emergent AEs are events that first occur or increase in severity after the first study drug dose. In case of repeated events in participants, the proportions on each treatment arm will use the number of participants as the denominator, and the number of participants with at least one event as the numerator, so each participants will be counted once. Incidence of AEs by treatment arm will

be compared using chi square tests.

AEs will be summarized by treatment arm, overall and by system organ class, severity, and relationship to study drug.

The following body systems will be summarized according to treatment arm:

- Any Treatment-Emergent AEs
- Blood and Lymphatic System Disorders
- Cardiac Disorders
- Ear and Labyrinth Disorders
- Eye Disorders
- Gastrointestinal Disorders
- General Disorders
- Hepatobiliary Disorders
- Immune System Disorders
- Infections and Infestations
- Injury, Poisoning and Procedural Complications
- Metabolism and Nutrition Disorders
- Musculoskeletal and Connective Tissue Disorders
- Nervous System Disorders
- Psychiatric Disorders
- Renal and Urinary Disorders
- Reproductive System and Breast Disorders
- Respiratory, Thoracic and Mediastinal Disorders
- Skin and Subcutaneous Tissue Disorders
- Surgical and Medical Procedures

AE listings will be sorted by treatment arm, then participant ID, and will include the following:

- Treatment Emergent (yes/no)
- AE # for the participant
- AE Primary Category
- AE Event Term
- AE Start Date
- AE Stop Date
- Days from Start of Study Medication
- Severity Grade
- Expected?
- Relationship to Study Drug
- Study Drug Action Taken
- Outcome

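### The SAP plans no by-arm liver table by multiple of ULN or worst post-baseline value and leaves unscheduled tests out of the laboratory summaries, so the ≥3 × ULN rate the protocol cites is not a planned output

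*SAP*

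**What the plan says.** **How the protocol describes liver risk**
- Section 6.1.9 warns of drug-induced liver injury, including fatal post-marketing cases, and gives the rate: "Patients treated with pirfenidone had a higher incidence of ALT and/or AST elevations of" at least 3 × ULN, 3.7% against 0.8% on placebo. It also asks for prompt liver tests when symptoms suggest injury.
- Table 1 in Section 6.1.5 sets bands for ALT or AST: above 3 and up to 5 × ULN, split by whether bilirubin exceeds 2 × ULN or there are signs or symptoms of liver injury, and above 5 × ULN. For the lowest band it adds: "Liver function tests should be repeated at 1 month intervals until" values are below 3 × ULN.
- Section 2.1.3.6 reports the pooled earlier trials by elevations above 3 × and above 10 × ULN and by Hy's law.
- Section 5.2 excludes patients with "Aspartate or alanine aminotransferase (AST/SGOT or AST/SGPT) > 3 X ULN". A participant may therefore enter with values above normal, up to 3 × ULN.

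**What the SAP plans**
- Clinical Laboratory Evaluations summarises scheduled tests: "Descriptive statistics will be presented by treatment group and visit week for the laboratory measurements". It then adds: "Continuous laboratory measures will also be compared to reference ranges to determine whether they are abnormally high, low, or normal". Shift tables and arm-coded plots are also planned.
- The same section says of unscheduled tests: "Unscheduled follow-up tests performed for medical or safety concerns, will be listed only".
- Adverse Events says AEs are summarised overall and by system organ class, severity and relatedness. It then introduces an explicit list: "The following body systems will be summarized according to treatment arm". The list has a row for hepatobiliary disorders but none for investigations or laboratory findings. Appendix C of the protocol counts an abnormal laboratory finding as a possible AE.

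**The concern.** Safety is part of the first study objective, and liver injury with fatal cases is among the risks the protocol describes. A reader of the final report will want to set this trial beside the protocol's 3.7% and 0.8%, and to know how many participants in each arm reached the Table 1 bands. None of the planned laboratory outputs gives that count.

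High/normal/low categories place 1.1 × ULN and 8 × ULN together. Symptom-prompted tests and Table 1 repeats can fall between visits, and their values enter listings only. The count could be built later from the listings, but the thresholds, the worst-value rule and the handling of unscheduled tests would then be chosen after unblinding, which is what a SAP exists to prevent.

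**Working it through.** **1. The plan's own safety figure.** Protocol Table 2A gives the chance of at least one event among 127 participants on pirfenidone, which is 1 − (1 − p)^127.

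| Rate p | Stated | Recomputed |
|---|---|---|
| 0.010 | 0.72 | 0.721 |
| 0.020 | 0.92 | 0.923 |
| 0.035 | 0.99 | 0.989 |

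The figures reproduce. They rest on 127 per arm; the SAP (Actual Sample Size) reports 123 randomized in total.

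**2. Expected cases at the actual size.** Inputs: 123 randomized, split 62/61 (assumed); rates of 3.7% and 0.8% from Section 6.1.9 (assumed to apply to RA-ILD).
- Pirfenidone: 62 × 0.037 = 2.3 participants at ≥3 × ULN.
- Placebo: 61 × 0.008 = 0.5.
- At least one on pirfenidone: 1 − 0.963^62 = 0.90. At least one on placebo: 1 − 0.992^61 = 0.39.
- With 61 on pirfenidone instead, the expected number is still 2.3 and the probability 0.90.
- If the true pirfenidone rate were 1%, the expected number is 62 × 0.01 = 0.6 and the probability of at least one is 0.46.

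**3. What one missed peak does.** One case out of an expected 2.3 is 1/2.3 = 43%. If two participants reach the threshold and one does so only at an unscheduled test, a count from scheduled tests gives 1/62 = 1.6% instead of 2/62 = 3.2%.

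**4. What the added table can show.** At 61 or 62 per arm, the two-sided 5% Fisher exact test has about 2% power for 3.7% versus 0.8%. At the planned 127 per arm (4.7 versus 1.0 expected) it would have been about 16%. A result of 2/62 has an exact 95% interval of 0.4% to 11.2%. The table is descriptive.

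**5. When scheduled liver tests occur.** Protocol Section 7.2.2 places them at Weeks 4, 8, 13, 19, 26, 39 and 52. They are 4 to 7 weeks apart up to Week 26 and 13 weeks apart after it. A short-lived rise in the second half-year can fall between scheduled tests.

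**6. The planned outputs against the missing count.**
- *By-visit statistics.* These include the maximum (SAP, Summary of Study Data), which is one value per arm and visit, not a number of participants. They do not pair aminotransferase with bilirubin in the same person. Routine laboratory tests are run locally (Protocol 7.1.1) and normal ranges are tabulated by center, so a pooled raw maximum need not convert to a multiple of ULN.
- *Shift tables.* Their categories are not stated. If they follow high/normal/low, a participant entering at 2.5 × and rising to 8 × ULN stays in the high category.
- *AE summaries.* These depend on the value being reported as an AE, and they carry no ULN threshold.
- *AEs leading to discontinuation.* This outcome is not liver-specific. It need not include the >3 to ≤5 × ULN band without bilirubin elevation or symptoms, for which Table 1 does not call for permanent discontinuation.

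**The case against.** The strongest reply is that the SAP does much more than sort values into three bins. By-visit statistics with a maximum and arm-coded plots would show an extreme scheduled value. AEs are tabulated by system organ class, severity and relatedness, with a hepatobiliary row. Deaths and SAEs have separate summaries, and AEs leading to discontinuation are a secondary outcome. Table 1 calls for permanent discontinuation above 5 × ULN, and above 3 × ULN with bilirubin elevation or symptoms, so the gravest cases have a by-arm route even when found off schedule. Keeping unscheduled tests out of visit-based tables is sound, because they are commoner in participants with abnormal values. With two or three cases expected, listings are informative.

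All of this stands, and it rules out several stronger readings that a reader might infer:
- *That the trial cannot report liver injury.* The data are collected and listed, and several AE routes exist. What is missing is a pre-planned count.
- *That an unscheduled finding is lost from every summary.* It is missing from the laboratory summaries only.
- *That peaks will mostly come from unscheduled tests.* The documents give no timing of elevations, and a Table 1 repeat may follow a scheduled result that is itself summarised.
- *That an enzyme rise recorded as an AE has no row but the overall total.* It also counts by severity and relatedness, and the general sentence on system organ class may cover it. The documents do not say where such a term would be coded. The explicit list and the general sentence simply do not match.

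The reply does not show that any planned output gives participants per arm at the protocol's thresholds, or brings off-schedule values into a laboratory summary. Low power is a reason to label the table descriptive, not to omit it.

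**Conclusion.** The point holds as a gap in planned reporting. The ≥3 × ULN rate and the Table 1 bands are not planned outputs, and an elevation seen only at an unscheduled test does not enter the laboratory summaries. The size is small in absolute terms: about 2.3 versus 0.5 participants, with a 0.90 chance of at least one pirfenidone case. Because the count is so small, one missed peak could be much of it.

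These numbers assume an even split of 123 and that 3.7% and 0.8% carry over to this population. How often a peak would be found only off schedule cannot be estimated from the documents. This is a cheap improvement to safety reporting and does not bear on the validity of the efficacy analysis.

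**What to change.** **SAP, Clinical Laboratory Evaluations.** Add one by-arm table for the Safety population, based on each participant's worst post-baseline value from scheduled and unscheduled tests together and using each site's own ULN. Show number and percent with:
- ALT or AST ≥3, >5 and >10 × ULN;
- total bilirubin >2 × ULN;
- ALT or AST ≥3 × ULN together with total bilirubin >2 × ULN.

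The first cut is set at ≥3 so that it matches the rate in Protocol 6.1.9; Table 1 starts just above 3, so the two differ only for a value of exactly 3 × ULN. Show each row by baseline category (≤ULN; >ULN to 3 × ULN). Keep the visit-based tables on scheduled results. Label the new table worst-case, because participants with abnormal values are tested more often, and state that it is descriptive.

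**SAP, Adverse Events.** Add an investigations/laboratory-findings heading, so that the explicit list agrees with the sentence that AEs are summarised by system organ class.

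**Cost.** Some SAP wording and one table, with no new data collection. No clinical threshold or management rule changes.

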### **Prior and Concurrent Medications**

Concomitant medication is defined as any medication a participant has received concurrently with study treatment. Prior Medication is defined as any medication or therapies initiated prior to date of first dose of study drug. Medications that are started prior to the date of first dose of study drug and continue after the first dose of drug are considered to be both prior and concomitant medications.

### **Reporting Conventions**

P-values  $\geq 0.001$  will be reported to 3 decimal places; p-values less than 0.001 will be reported as “<0.001”. The mean, standard deviation, and any other statistics other than quantiles, will be reported to one decimal place greater than the original data. Quantiles, such as median, or minimum and maximum will use the same number of decimal places as the original data. Estimated parameters, not on the same scale as raw observations (e.g. regression coefficients) will be reported to 3 significant digits.

### **Unblinding**

Study Center Level Unblinding: A minimum number of personnel will see the randomization table and treatment assignments before the study is complete. The treatment assignments will be

blinded to participants and investigators until the end of the study. Emergency un-blinding for AEs may be performed ONLY if the participant's well-being requires knowledge of the participant's treatment assignment. The investigator should make every effort to contact the study team prior to un-blinding a participant's treatment assignment.

Sponsor/Trial Level Unblinding: The study team will remain blinded to treatment assignments until all participants have completed the study and the database has been finalized and locked for analysis.

## **Quality Assurance of Statistical Programming**

Programs and anonymized datasets will be stored on a server at Brigham and Women's Hospital that has nightly back-up. To provide high quality code that is understandable, and allows reproduction of the analysis the following will be explicitly stated:

- Author
- Date of writing
- Description of the code's purpose, e.g. to create the analytic dataset, to analyze the primary outcome variable, etc.
- List of steps or strategy to achieve purpose of code
- References to inputs and outputs
- Reference to any parent code file that runs the child code file
- Population to be used in a table or figure will be explicitly set at the start of a block of code that computes the output.

